1.6. Study Design

This study will be an open label, multi-cohort, phase II trial for the combination therapy of MEDI0457 (INO-3112) and Durvalumab (MEDI4736) in patients with HPV-16 and/or -18 related malignancies. This study will enroll 3 cohorts of patients with HPV-16/18 (+) tumors. The three cohorts are:

- 1. HPV-16/18 cervical cancer,
- 2. HPV-16/18 rare tumors (anal, penile, vulvar, vaginal), and
- 3. HIV (+) HPV-16/18 malignancies (any site).

Each cohort will have a two-stage design with predetermined stopping rules based on ORR after stage I and each cohort will function independently clinically. After each cohort completes accrual to stage I, only the two cohorts with the most responses will move on to stage 2.

Therefore, accrual to stage 2 will not start till all three cohorts have completed stage I. However, if a single cohort has a high response rate (≥4 responses out of 9 patients), the second stage of accrual may proceed prior to other cohorts completing stage I.

At the onset of the study, only patients with cervical, vulvar, or vaginal cancers will be enrolled for the first 3 slots. Once all 3 of these patients have completed the first 6 weeks of treatment, enrollment will be opened to all included cancer histotypes.

Both MEDI0457 and durvalumab treatment will continue until confirmed disease progression or unacceptable toxicity. Either treatment may be stopped by the investigator if a SAE is deemed to be related to that treatment while the other treatment continues.

The target population consists of male or female patients 18 years of age or older with recurrent or metastatic HPV 16- or 18-associated cancers with persistent or progressive disease (PD) after initial standard-of-care treatment and lacking a curative treatment option.

Eligible patients must have at least one "measurable target lesion"—according to RECIST version 1.1—that has not been previously irradiated. In addition, if the primary lesion is not large enough for a biopsy without changing radiologic findings for following response, one additional lesion

Version Number: 1.8 Date: July 26, 2019

Proprietary of MD Anderson Cancer Center

that can be safely biopsied at screening and prior to the first dose of MEDI0457 at Week 1 will be required.

All patients will receive combination treatment with MEDI0457 and durvalumab as per the **Planned Dosing Schedule (Section 4.4.1, Figure 1**, and **Table 3**).

[figure not shown]

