3.4. Discontinuation of Investigational Product

An individual patient will not receive any further IP if any of the following occur.

- Initiation of subsequent anticancer therapy including another investigational agent.
- Confirmed PD: the initial assessment of PD by RECIST v1.1 (baseline PD assessment) will be confirmed by a repeat evaluation at the next tumor assessment time point, but no sooner than 4 weeks later. If any tumor assessment time point (beyond the first PD assessment) shows ≥ 20% increase in the overall tumor burden (the sum of diameters of target lesions and new lesions), when compared to the baseline PD assessment (the sum of diameters of target lesions and new lesions), the patient would be deemed as having confirmed PD and must be discontinued.
- An AE that, in the opinion of the Investigator, supporting company, or the MDACC IND Office, contraindicates further dosing.
- Patient experienced a DLT as defined in Section 6.7.2.
- Withdrawal of consent from further treatment with IP or lost to follow-up.

Version Number: 1.8 Date: July 26, 2019

Proprietary of MD Anderson Cancer Center

- Patient is determined to have met one or more of the exclusion criteria or failed to meet all of the inclusion criteria for study participation and continuing to receive IP might constitute a safety risk.
- Pregnancy or intent to become pregnant.
- Non-compliance with the study protocol that, in the opinion of the Investigator, supporting company, or the MDACC IND Office, warrants withdrawal from treatment with IP (e.g., refusal to adhere to scheduled visits).
- The treating Physician determines it is not in the best interest of the patient to continue.

At any time, patients are free to discontinue IP or withdraw from the study (i.e., IP and assessments) without prejudice to further treatment. If a patient is withdrawn from study, see Section 3.5.2.

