4.4. Doses and Treatments

4.4.1. Planned Dosing Schedule

All patients will receive combination treatment with MEDI0457 and durvalumab as per the following **Planned Dosing Schedule** (treatment should be given at the beginning of the week, unless otherwise specified) as detailed in **Figure 1** and **Table 3**.

Durvalumab will be administered at a fixed dose of 1500 mg q4wk for patients that are \ge 30 kg. For patients who weigh <30 kg, weight-based dosing will be used at a dose of 20 mg/kg q 4 weeks, and if their weight increases to \ge 30 kg they can be switched to durvalumab at 1500 mg every 4 weeks.

Patients will receive 7 mg MEDI0457 delivered by IM followed by EP on Day 1 (Week 1), Week 3, Week 7, Week 12 and then every 8 weeks until disease progression or unacceptable toxicity. Durvalumab will be administered on Week 4, Week 8, Week 12 and then every 4 weeks until disease progression or unacceptable toxicity. On days when both MEDI0457 and durvalumab administrations will occur on the same day (Week 12 then every 8 weeks), MEDI0457 will be administered first, and durvalumab IV infusion will start approximately 1 hour after MEDI0457 is delivered intramuscularly followed by EP.

Minimum time between Week 3 MEDI0457 dose and the Week 4 first durvalumab dose, and the Week 7 MEDI0457 dose and the Week 8 durvalumab dose is 7 days.

Version Number: 1.8 Proprietary of MD Anderson Cancer Center Page 1019 26 2019

4.4.2. **Durvalumab**

Durvalumab will be administered at a fixed dose of 1500 mg q4w in the combination and monotherapy arms for patients weighing \geq 30 kg. For patients weighing \leq 30 kg, the dose will be 20 mg/kg. The maximum number of doses of checkpoint inhibitor therapy will equal 13.

The duration will be approximately 1 hour (± 5 minutes) for each durvalumab infusion. A 1- hour observation period is required after the first infusion of durvalumab is administered. If no clinically significant infusion reactions are observed during or after the first dose, subsequent infusion observation periods can be at the investigator's discretion (suggested 30 minutes after each durvalumab infusion).

Patients will be monitored during and after the infusion with assessment of vital signs at the times specified in the study protocol.

See Section 6.7.1 dose administration changes in the event of Grade 1 or 2 infusion-related reactions.

4.4.3. **MEDI0457**

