6.7. Management of IP-related Toxicities

6.7.1. **Dose Management**

Either treatment may be stopped by the investigator while the other treatment continues. MEDI0457 doses should not be modified.

For AEs that are considered at least partly due to administration of durvalumab the following dose adjustment guidance may be applied:

- Treat each of the toxicities with maximum supportive care (including holding durvalumab).
- If the symptoms promptly resolve with supportive care, consideration should be given to continuing the same dose of durvalumab along with appropriate continuing supportive care. If medically appropriate, dose modifications are permitted for durvalumab.
- All dose modifications should be documented with clear medical reasoning and documentation of the approach taken.

In addition, there are certain circumstances in which durvalumab should be permanently discontinued (Appendix D, Postow 2015).

Following the first dose of durvalumab, subsequent administration of durvalumab can be modified based on toxicities observed (Appendix D, Postow 2015). All toxicities will be graded according to NCI CTCAE version 4.03.

Based on the mechanism of action of durvalumab leading to T-cell activation and proliferation, there is the possibility of observing irAEs during the conduct of this study. Potential irAEs include immune-mediated dermatitis, hepatitis/hepatotoxicity, endocrinopathy (hypothyroidism, hyperthyroidism, hypophysitis, and adrenal insufficiency), neuropathy/neuromuscular toxicity, nephritis, pancreatitis (elevated lipase/amylase), pneumonitis, and colitis. Patients should be monitored for signs and symptoms of irAEs. In the absence of an alternate etiology (e.g., infection or PD) signs or symptoms of dermatitis, hepatitis/hepatotoxicity, endocrinopathy

Version Number: 1.8

Proprietary of MD Anderson Cancer Center Date: July 26, 2019

(hypothyroidism, hyperthyroidism, hypophysitis, and adrenal insufficiency), neuropathy/neuromuscular toxicity, nephritis, pancreatitis (elevated lipase/amylase), pneumonitis, and colitis should be considered to be immune-related.

Dose modifications will not be required for AEs that are clearly not attributable to durvalumab (such as an accident) or for laboratory abnormalities that are not deemed to be clinically significant. Administration may continue despite concurrent vitiligo of any AE grade.

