Acetaminophen and/or an antihistamine (e.g., diphenhydramine) or equivalent medications per institutional standard may be administered prior to infusion at the discretion of the investigator for primary prophylaxis against infusion-related reactions. In the event of Grade ≤ 2 infusion-related reaction, the infusion rate of durvalumab may be decreased by 50% or interrupted until resolution of the event (up to 4 hours) and re-initiated at 50% of the initial rate until completion of the infusion. In patients experiencing Grade ≤ 2 infusion-related reaction, subsequent infusions may be administered at 50% of the initial rate. If a patient experiences an infusion-related reaction, acetaminophen and/or an antihistamine (e.g., diphenhydramine) and/or corticosteroid or equivalent medications per institutional standard may be administered prior to subsequent infusions at the discretion of the investigator for secondary prophylaxis of infusionrelated reactions. If the infusion-related reaction is Grade 3 or higher in severity, treatment with durvalumab will be discontinued.

As with any antibody, allergic reactions to dose administration are possible. Appropriate drugs and medical equipment to treat acute anaphylactic reactions must be immediately available, and study personnel must be trained to recognize and treat anaphylaxis. The study site must have immediate access to emergency resuscitation teams and equipment in addition to the ability to admit patients to an intensive care unit if necessary.

6.7.2. **Dose-limiting Toxicities**

Grading of DLTs will be according to the NCI CTCAE version 4.03.

A DLT will be defined as any Grade 3 or higher treatment-related toxicity that occurs during the DLT evaluation period (i.e., 4 weeks after the first dose of durvalumab is administered for the initial six patients), including the following treatment-related toxicities:

- a. Any Grade 4 irAE is a DLT.
- b. Any \geq Grade 3 colitis is a DLT.
- c. Any \geq Grade 3 non-infectious pneumonitis irrespective of duration is a DLT.
- d. Any Grade 2 pneumonitis that does not resolve to \leq Grade 1 within 3 days of the initiation of maximal supportive care is a DLT.
- e. Any \geq Grade 3 neurotoxicity (to include but not limited to limbic encephalitis, autonomic neuropathy, including peripheral neuromotor syndromes such as myasthenia gravis and Guillain-Barré) irrespective of duration is a DLT.

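### Appendix D gives resume instructions for some DLTs after which Section 3.4 bars all further study drug, and the six-patient DLT window in 6.7.2 does not fit the 34-patient toxicity rule

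*Combined protocol and SAP*

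**What the plan says.** **Individual stopping rule.** Section 3.4 says that a patient gets no further investigational product (IP) after any of a list of events. One is "Patient experienced a DLT as defined in Section 6.7.2". The stop covers both MEDI0457 and durvalumab.

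**DLT definition.** Section 6.7.2 covers treatment-related toxicity in a window of "4 weeks after the first dose of durvalumab is administered for the initial six patients". Four items matter here:
- Item a: "Any Grade 4 irAE is a DLT".
- Item e: Grade 3 or higher neurotoxicity, a class that extends to "peripheral neuromotor syndromes such as myasthenia gravis and Guillain-Barré) irrespective of duration is a DLT".
- Item h: other Grade 3 or higher immune-related events that do not fall to Grade 2 within 3 days, or to Grade 1 or baseline within 14 days.
- Item k: a Grade 3 or higher injection site reaction that lasts beyond 5 days or does not fall to Grade 1 in 14 days.

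**Toxicity management.** Section 6.7.1 states "Following the first dose of durvalumab, subsequent administration of durvalumab can be modified based on toxicities observed" and refers to Appendix D, both for modification and for permanent discontinuation. It also states "Either treatment may be stopped by the investigator while the other treatment continues". Section 1.6 has a similar sentence for related SAEs: "Either treatment may be stopped by the investigator if a SAE is deemed to be related to that treatment while the other treatment continues".

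**Trial-level rule.** Section 8.1.3 monitors DLTs in groups of six for all 34 patients of each cohort. It stops at 4/6, 6/12, 9/18, 11/24 or 13/30, and toxicity reports are due after every six evaluable patients. Table 5 gives the operating characteristics.

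**The concern.** A clinician managing a toxicity will open the row for that event in Appendix D or E, not the discontinuation list in 3.4. If the row says to resume on recovery and the event is a DLT, the site has two instructions that cannot both be followed. Neither 6.7.1, 6.7.2 nor Appendix D refers back to 3.4. At stake is re-exposure after a DLT, in a combination that the protocol (1.3.1) describes as being studied for the first time in this population.

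The window wording raises a second problem. If a DLT can be recorded only in six patients, a rule that counts DLTs up to patient 30 has nothing to add after its first look.

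**Working it through.** **1. DLT items against the appendices**

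| Event in the DLT window | 6.7.2 | Appendix instruction | Consistent with 3.4? |
|---|---|---|---|
| Grade 3 neurotoxicity | DLT of any duration (e) | Table 7: hold, then resume at the next dose on recovery to Grade 1 or baseline | No |
| Grade 4 endocrinopathy other than hypothyroidism | DLT (a); exclusion b covers only asymptomatic Grade 3 | Table 7: hold, resume once controlled | No |
| Immune-related Grade 3 rash missing the 3-day or 14-day limit | DLT (h) | Table 7: resume on recovery, without those limits | No |
| Immune-related transaminases above 5 and up to 8 x ULN missing those limits | DLT (h; hepatitis is not among its exclusions) | Table 7: resume on recovery; Hy's Law cases stop permanently | No, outside Hy's Law |
| Grade 3 injection site reaction reaching Grade 2 within 5 days but not Grade 1 in 14 days | DLT (k) | Appendix E: omit the next vaccine dose; durvalumab may continue after discussion with the medical monitor | No |
| Grade 3 or 4 pneumonitis or diarrhea; transaminases above 8 x ULN | Pneumonitis c; colitis b; transaminases i | Table 7: discontinue permanently | Yes |

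The first row is the firmest. The Grade 3 or 4 endocrine cell also has a line that only permits resumption, and in the extracted text it runs together with its neighbour. The Grade 3 cell for Guillain-Barré and myasthenia gravis is merged in that text and is not relied on.

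**2. Reproducing the toxicity rule as planned**

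Inputs (8.1.3): prior Beta(0.6, 1.4); stop if Pr(DLT rate > 0.30 | data) > 0.90; looks at 6, 12, 18, 24 and 30; maximum 34.

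Boundary at n: the smallest x with 1 - F(0.30; 0.6 + x, 1.4 + n - x) > 0.90, where F is the Beta distribution function. This gives 4, 6, 9, 11 and 13, with posterior probabilities 0.945, 0.905, 0.951, 0.938 and 0.929. One DLT fewer gives 0.800, 0.772, 0.883, 0.871 and 0.863. The stated boundaries are correct.

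An exact sequential binomial calculation with all patients counted gives P(stop) of 0.002, 0.033, 0.196, 0.555 and 0.875 at true rates 0.10 to 0.50. Table 5 has 0.002, 0.035, 0.196, 0.549 and 0.877. Table 5 therefore assumes that patients after the sixth can contribute DLTs.

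**3. The literal six-patient window**

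Assumption: six per cohort, because 6.7.2 does not say whether six is per cohort or overall. With DLTs possible only in the first six, 6/12 would need six DLTs among them, which already crosses 4/6. Counts of 9, 11 and 13 cannot be reached. So P(stop) = P(X >= 4), X ~ Bin(6, p):

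- p = 0.30: 15(0.3^4)(0.7^2) + 6(0.3^5)(0.7) + 0.3^6 = 0.0595 + 0.0102 + 0.0007 = 0.070
- p = 0.40: 0.1382 + 0.0369 + 0.0041 = 0.179
- p = 0.50: 22/64 = 0.344

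| True DLT rate | Table 5 P(stop) | Literal six |
|---|---|---|
| 0.30 | 0.196 | 0.070 |
| 0.40 | 0.549 | 0.179 |
| 0.50 | 0.877 | 0.344 |

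**4. Ceiling on re-dosing**

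Section 4.4.2: "The maximum number of doses of checkpoint inhibitor therapy will equal 13". One dose opens the window, so a patient who resumed could receive at most 13 - 1 = 12 further durvalumab doses.

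**The case against.** **The texts are not of equal force.** Section 3.4 is absolute. Section 6.7.1 introduces the durvalumab rules as guidance that may be applied, and Table 7 recommends that management follow it. On an ordinary reading, 3.4 prevails. This stands as to likely intent. It does not close the gap, because no text states the precedence and 6.7.1 sends sites to Appendix D to learn when durvalumab stops permanently.

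**Safeguards exist.** Adverse events of special interest, which include the immune-related and administration-site events above, are reported within 24 hours (7.5). Hepatic abnormalities are reported within 24 hours, and dosing is interrupted if no diagnosis is established (7.6.4). Grade 3 injection site reactions are discussed within 72 hours as to whether dosing should continue (7.6.6). The neurotoxicity row calls for Study Physician discussion and a neurology consult. All of this lowers the chance of an unnoticed re-dose, but none of it applies the DLT stop.

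**The window wording is editorial.** Section 8.1.3 names all 34 patients and calls for reports after every further six. That is right about intent, and it supports correcting 6.7.2. Also, a cohort that ends at nine patients has only the 4/6 look, so both readings then agree, and by design (8.1.1) at most two cohorts go beyond nine.

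**Stronger readings that a reader might infer.** One is that the protocol requires re-dosing after DLTs; the guidance wording and the unconditional stop in 3.4 do not support that. Another is that toxicity monitoring ends at patient six or that Table 5 is wrong; 8.1.3 contradicts the first, and the recalculation confirms Table 5. A third is that the two harms add up, which the verdict addresses.

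**Conclusion.** The point holds as an inconsistency between stated rules. It is firm for treatment-related Grade 3 neurotoxicity, and it extends to the other events marked as inconsistent above. It is limited to DLTs in the 4 weeks after the first durvalumab dose, about Week 4 to Week 8.

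The number of patients affected cannot be estimated from the documents. Twelve further durvalumab doses is a per-patient ceiling that needs recovery, no progression and a full course; it is not an expected effect.

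The two effects are alternatives. If six is literal, the re-dosing conflict is confined to those six patients, but the later toxicity looks are disabled and P(stop) at a true rate of 50% falls from 0.877 to 0.344. If all patients are meant, as 8.1.3 indicates, the rule performs as in Table 5 but the conflict reaches every patient. The literal figures assume six per cohort and a cohort that would otherwise run to 34.

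The response-rate analysis and the planned sample size are not affected. The wording should be corrected.

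**What to change.** 1. In 6.7.2, delete the restriction to the first six patients, so that the 4-week window applies to every patient in each cohort, in line with 8.1.3 and Table 5.
2. In 6.7.1 and at the head of Appendices D and E, add one sentence: an event that meets the 6.7.2 DLT definition is handled under 3.4, with no further MEDI0457 or durvalumab, and the appendices govern all other events. The sentence should say that this also overrides the statements in 1.6 and 6.7.1 that one treatment may continue when the other is stopped.

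The cost is one deletion and one sentence in three places, with no added patients, visits or tests. The downside is that some patients whose DLT resolves lose the option to resume.

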3.5. Criteria for Withdrawal

A patient will be considered to have completed the study when he/she completes all protocol specified scheduled study visits. The follow-up visit will be the last study visit.

If a patient discontinues or is withdrawn at any time after initiation of study treatment, the investigator should make every effort to have the patient complete all assessments designated for the follow-up visit. The investigator will make every effort to have all scheduled assessment blood samples collected as indicated in **Table 3**. Any AEs present at the time of discontinuation/withdrawal should be followed in accordance with the safety requirements outlined in Section 7.

Patients who discontinue study treatment will be followed for: (1) up to 90 days after last study treatment with durvalumab and/or MEDI0457; (2) until AE/SAE resolution or an outcome is reached for all events (see Section 7.4.2); or (3) until patient initiates alternative anticancer therapy. Patients who leave the study because of a serious or significant safety issues should be followed closely until the AEs are fully and permanently resolved or stabilized (if complete resolution is not anticipated), with the follow-up data recorded in the database (see Section 7.4.2 for further details regarding the follow-up of unresolved AEs).

If a patient discontinues from treatment for reasons other than disease progression, and therefore continues to have tumor assessments, drug or procedure-related SAEs must be captured until the patient is considered to have confirmed PD and will have no further tumor assessments.

Investigator should discuss the reason for any discontinuation of study treatment with the MDACC IND Office Medical Monitor prior to any action or within 24 hours when information becomes available.

The primary reason for the patient discontinuing study treatments or withdrawal from the study should be among the following standard categories.

• Adverse Event: Clinical or laboratory events occurred that, in the medical judgment of the investigator for the best interest of the patient, are grounds for discontinuation. This includes serious and non-serious AEs regardless of relation to study treatment.

Version Number: 1.8
Date: July 26, 2019

Proprietary of MD Anderson Cancer Center

• Death.

- Withdrawal of Consent: The patient desired to withdraw from further participation in the study in the absence of an investigator-determined medical need to withdraw. If the patient gave a reason for withdrawal, it should be recorded in the database. This reason does not allow for further data collection and should not be selected if follow-up data collection of this patient is anticipated by the patient.
- Lack of Patient Compliance: The patient's findings or conduct failed to meet the protocol entry criteria or failed to adhere to the protocol requirements (e.g., treatment non-compliance, failure to return for defined number of visits). The violation should be discussed with the IND Office Medical Monitor prior to discontinuation of study treatments or study withdrawal.
- Lost to Follow-up: The patient fails to attend study visits and study personnel are unable to contact the patient after repeated attempts including letter sent by certified mail or equivalent.
- Physician Decision: The patient was terminated for a reason other than those listed above by the physician caring for the patient.
- Other: The patient was terminated for a reason other than those listed above, such as termination of study by the supporting company.

